4.3 Final Follow-up and End of Participation (Day 10)

At the final follow-up, the following information will be collected

- Length of time device worn for since fitting (hours)
- Adhesion to patient's leg (rate from very well to not at all)
- Use of additional fixation to keep the device in position
- Ease of re-application if removed
- Patient comfort (rate from very comfortable to extremely uncomfortable)
- Patient sleep post-fitting
- Patient's current mobility

Once the final follow-up has been completed the patient's participation will end and the patient will be exited from the study.

See Table 1 for full schedule of events.

Procedure / Assessment	Baseline (Day 0)	Follow-up (Days 1-10)
Confirmation of eligibility	X	
Informed Consent	X	
Demographics (age in years, date of birth, gender, date of stroke diagnosis, mobility, adjunctive treatments to the geko™ device e.g. drugs, stockings	X	
Bilateral fitting of geko™ devices as per standard care	X	X
Ease of fitting	X	X
Adhesion to patient's leg	X	X
Additional fixation	X	X
Ease of re-application if device removed	X	X
Patient comfort post fitting	X	X
Device setting	X	X
Patient sleep post-fitting	X	X
Hours of wear since fitting	X	X
Patient mobility	X	X
Assess for AEs	X	X

Table 1: Schedule of Events.

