4.2 Follow-up and Daily Application of geko™ therapy (Days 1-9)

During daily review of the patient by a member of the healthcare team, a new geko™ device will be fitted bilaterally as per standard care. In addition, the following information will be collected each day or until the patient is able to mobilize independently:

- Length of time device worn for since fitting (hours)
- Adhesion to patient's leg (rate from very well to not at all)
- Use of additional fixation to keep the device in position
- Ease of re-application if removed
- Patient comfort (rate from very comfortable to extremely uncomfortable)
- Patient sleep post-fitting
- Patient's current mobility

Fit new geko™ device bilaterally for VTE prevention as per hospital standard care. Devices fitted will be as per allotted patient group and study phase and the following post-application information recorded:

- Ease with which device fitted (rate from very easy to impossible)

- Adhesion to patient's leg (rate from very well to not at all)
- Use of any additional fixation to keep the device in position.
- Patient comfort (rate from very comfortable to extremely uncomfortable)
- Device setting (1-11)
- Assess for any AEs

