5.2 Premature Withdrawal / Discontinuation

All patients have the right to withdraw at any point without prejudice to their treatment. If necessary, the Investigator may discontinue a patient at any time if it is considered medically necessary e.g. loss of mental capacity. The Investigator may also withdraw a patient if it is considered that the scientific, and therefore, ethical standards of the study are compromised. In addition, patients will be withdrawn from the study, at the Investigator's discretion, if they fail to wear the geko™ device as part of their standard care as directed by the treating physician. The reasons for withdrawal will be fully recorded in the patient's source documents and on the appropriate case report form.

If a participant is prematurely discontinued from the study at any time due to an adverse event (AE) or serious adverse event (SAE), the procedures stated in Section 9.0 must be followed.

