7.4 Application of geko™ Device and Collection of Device Performance Data

Patients will receive treatment with either the geko™ T3 or XT-3 device as part of their standard care for VTE prevention as per hospital clinical protocol. During daily review of the patient by a member of the healthcare team, the following information will be collected for a maximum of 10 days or until the patient is able to mobilize independently:

- Length of time device worn for since fitting (hours)
- Adhesion to patient's leg (score from very well to not at all)
- Use of additional fixation to keep the device in position.
- Patient comfort
- Patient sleep post-fitting
- Patient's current mobility
- Ease with which device fitted (score from very easy to impossible)
- Device setting
- Assess for any AEs

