10.0 Direct Access to Source Data / Documentation

Data will be collected on paper case report forms (CRFs) by appropriately trained delegated members of the patient's healthcare team at the clinical site. Only designated members of the team will be allowed to record and / or correct data in the CRFs. CRFs

will be provided by the Sponsor to the site for completion together with CRF completion guidelines. All CRFs for the study, can be found in Appendix 3 of this protocol. Patients will be assigned a unique study identification number (participant number and initials) and will be identified only by this unique identifier on CRFs and on source documents by name and date of birth. No personal identifier will be used in any publication or communication used to support this research study. The participant identification number will be used if it becomes necessary to identify data specific to a single participant. The monitors, auditors, personnel authorised by the Sponsor, the local IRB, and regulatory agencies are eligible to review medical and research records related to this study as a part of their responsibility to protect human participants in clinical research and will be given direct access to source data and documentation (e.g., medical charts/records, printouts etc.) for source data verification, provided that participant confidentiality is maintained in accordance with local requirements. Access to electronic medical records may be governed by institution policy and each site will be required to ensure access while remaining compliant with institutional requirements.

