Day 10 final assessment and patient participation completed. Please complete Exit CRF

CASE REPORT FORM	FINAL FOLLOW-UP 10 (DAY 10)		DATE (DD/MM/YYYY)	____ / ____ / _____
STUDY SITE: PRINCIPAL INVESTIGATOR:	THE ROYAL STOKE UNIVERSITY HOSPITAL [name]			

SITE NUMBER

0	2	5
---	---	---

 PATIENT NUMBER

0		
---	--	--

 PATIENT INITIALS

--	--

CRF completed by:

Print Name: _____ Signature: _____ Date: ____ / ____ / _____

To be completed by Principal Investigator:

I am confident that the information supplied in this case record form is complete and accurate data.

Signature: _____ Date: ____ / ____ / _____

Exit Day 10

CASE REPORT FORM	EXIT			DATE (DD/MM/YYYY)	____ / ____ / ____					
STUDY SITE:	THE ROYAL STOKE UNIVERSITY HOSPITAL									
PRINCIPAL INVESTIGATOR:	[name]									
SITE NUMBER	0	2	5	PATIENT NUMBER	0			PATIENT INITIALS		
Study Exit Date (DD/MM/YYYY)	____ / ____ / ____									
Date of Last Assessment (DD/MM/YYYY)	____ / ____ / ____									
Last Assessment Completed	Baseline  Follow-up 1  Follow-up 2  Follow-up 3  Follow-up 4  Follow-up 5  Follow-up 6  Follow-up 7  Follow-up 8  Follow-up 9  Follow-up 10 									
Reason for Exit from Study	Study completed  Lost to follow-up  Non-compliance  Medical contraindication  Consent withdrawn  Other** 									
**Additional explanation required:										

CRF completed by:

Print Name: _____ Signature: _____ Date: ____ / ____ / ____

[figure not shown]
To be completed by Principal Investigator:

I am confident that the information supplied in this case record form is complete and accurate data.

[figure not shown]
Signature: _____ Date: ____ / ____ / ____

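### Table 1 schedules AE assessment to Day 10, but Section 4.3 and the Day 10 and Exit CRFs have no AE item, so events in the last wear period are not solicited

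*Combined protocol and SAP*

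**What the plan says.** Two places call for AE assessment throughout follow-up:

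- Table 1 has a row "Assess for AEs", marked at baseline and in the single follow-up column covering Days 1-10.
- Section 7.4 states that "the following information will be collected for a maximum of 10 days or until the patient is able to mobilize independently", and AE assessment is the last entry in the list that follows.

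The day-by-day text and the forms are narrower:

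- Section 4.1 (Day 0) and Section 4.2 (Days 1-9) include an AE check. In Section 4.2 it belongs to the second block, introduced by "the following post-application information recorded", which describes the newly fitted device.
- Section 4.3 (Day 10) begins "At the final follow-up, the following information will be collected" and lists hours worn, adhesion, extra fixation, re-application, comfort, sleep and mobility. It has no AE entry.
- In Appendix 3, the Day 0 form and the common Day 1-9 form ask about AEs since consent. The Day 10 form does not. It ends with a general comments box and the line "Day 10 final assessment and patient participation completed. Please complete Exit CRF".
- The Exit form records dates, the last assessment and an item headed "Reason for Exit from Study". It has no AE question.

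On whether other forms exist, Section 10.0 says: "All CRFs for the study, can be found in Appendix 3 of this protocol".

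**The concern.** AE incidence (all, serious, treatment-related and device-related) is the whole secondary endpoint set in Sections 2.1.2 and 8.4.2. An incidence is only as complete as the asking behind it. If the last assessment has no AE question, a blank for the final wear period could mean that nothing happened or that nobody asked, and the database cannot tell the two apart. Staff who follow Section 4.3 and the forms exactly will leave out an assessment that Table 1 requires.

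The type of event most likely to matter here is local. Section 1.3 presents reduced skin irritation as an expected benefit of KM40C, and irritation at the contact area is the only side effect listed in Appendix 4. The Day 10 removal is the last chance to notice it.

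**Working it through.** The plan states no figure on this point, so the check is a comparison of texts and a count.

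**1. Requirement against implementation**

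| Source | Day 0 | Days 1-9 | Day 10 | Exit |
|---|---|---|---|---|
| Table 1 | AE marked | AE marked | AE marked (Days 1-10 column) | no column |
| Sections 4.1-4.3 | AE listed | AE listed | not listed | not described |
| Appendix 3 forms | AE question | AE question | none | none |

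The conflict is in the Day 10 column.

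**2. How the item probably dropped out.** Section 4.2 has two blocks: one on the device coming off and one on the device going on. The seven items of Section 4.3 match the first block. The AE check is in the second, which does not recur on Day 10 because no new device is fitted. This is an inference from the layout, but it suggests an oversight and not a decision to stop asking.

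**3. Forms for a patient who completes Day 10**

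- Forms: 1 (Day 0) + 9 (Days 1-9) + 1 (Day 10) + 1 (Exit) = 12.
- With an AE question: 1 + 9 = 10.
- Without one: 12 − 10 = 2, the Day 10 and Exit forms.

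**4. Wear periods**

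- Devices are fitted on Days 0 to 9, giving 10 wear periods, the last running from Day 9 to Day 10.
- The questions on Days 1 to 9 follow the first 9.
- Not followed by a question: 10 − 9 = 1, and 1/10 = 10%.

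**5. Does the look-back wording close the gap?** The daily question covers everything since consent, so each day's answer can pick up events missed earlier. It is last asked on Day 9 and cannot reach past that point. What goes unsolicited is any event arising after the Day 9 assessment, and nothing before it.

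**6. Early exit.** On the Day 1-9 form the mobility item sends a patient who can walk independently to the Exit form, and the AE question comes later on that same form. Staff might stop there, in which case that patient's last wear period would also go unasked. The form does not say to leave the remainder blank, and the documents do not say how many patients leave this way. No size can be attached to this part.

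**7. After the fix.** With the question on the Day 10 form, coverage for a completer rises from 9 of 10 to 10 of 10 wear periods. On the Exit form it also covers early leavers, whichever way the mobility item is read.

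**The case against.** The strongest reply is that the protocol already requires the Day 10 assessment. Section 4.3 refers to Table 1 for the full schedule, and Table 1 marks AEs through Day 10. That is right, and a reader who inferred that the plan omits Day 10 AE assessment altogether would be going too far. What is missing is the list entry and the form field. Table 1 is also loosely drawn: it marks device fitting and setting through Day 10, and hours of wear and sleep at baseline. The 10 days in Section 7.4 could be read as Days 0-9. This makes the contradiction less sharp, but the Table 1 column names Day 10, and an AE check makes sense at a final visit in a way that a new fitting does not.

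Second, Appendix 3 is headed as sample forms, and Section 11.4 requires deviations to be recorded in the CRFs although no form shown has a field for them. The set may therefore be incomplete. Section 10.0 points the other way. The safe statement is that no form shown solicits these events.

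Third, other routes remain. The medical record is the primary source, and CRFs are monitored against source documents. A device-related event must reach the sponsor within 24 hours once the physician knows of it. The Day 10 form has a comfort rating and comment boxes. An event could therefore still surface, but none of these routes is an AE question.

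Two further inferences are not supported:

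- A reader might treat the missing adverse-event exit reason as leaving such withdrawals unrecorded. The form offers a medical contraindication box and an 'other' box with explanation required. Section 5.2 separately requires reasons to be recorded and the Section 9.0 procedures to be followed.
- A reader might call the lack of a skin item a broken commitment. The objective is adhesion, no endpoint grades skin, and irritation can be reported under the general AE question.

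**Conclusion.** The point stands as an internal inconsistency with a modest effect on data completeness. For every Day 10 completer, AEs arising in the last of 10 wear periods are not solicited on any form shown. The same may be true for patients who exit at the mobility item, but that is possible and not established.

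The consequence is confined to the descriptive secondary AE summary. No between-group AE test is planned. The gap is identical in both groups for completers, so the documents give no ground for saying that it favours one hydrogel. The adhesion endpoint is unaffected. The number of AEs that might be missed cannot be estimated from the documents.

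The conclusion assumes that devices are fitted on Days 0-9, that the Appendix 3 forms are used as shown, and that the Table 1 follow-up column means what its Days 1-10 label says. Because the repair is nearly free and protects the only secondary endpoint set, it should be made.

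**What to change.** 1. Add AE assessment to the Section 4.3 list, matching Section 4.2.
2. Copy the existing AE question, unchanged, to the Day 10 CRF and the Exit CRF.
3. Use the revised forms from the first Group 1 patient. The cohorts run one after the other (Section 3.0, T3 first). A change made between phases would mean that XT-3 patients were asked more often than T3 patients, turning an equal gap into an unequal one.

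Optional:

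- An adverse-event tick box among the exit reasons, to make such exits easier to count.
- A short prompt about skin at the contact site when the device is removed, since irritation is the listed side effect and its reduction is the stated advantage of KM40C. This is an addition to the plan and not a repair.

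The required changes cost one list entry and one question on two forms, plus a protocol amendment if made after approval. They need no new procedure. The skin prompt would add a line to the forms and would probably bring in more mild skin reports in both groups, still rated by unblinded staff.

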Very Comfortable 	Comfortable 	Uncomfortable 	Very Uncomfortable 	Extremely Uncomfortable 

If any discomfort has been indicated, please provide a comment below:

Did the patient sleep with the device on?		Yes 	No 
---	--	------------------------------	-----------------------------

DAY 1: Application of geko™ device

Current mobility - Is patient able to walk independently? (If YES is selected patient CANNOT continue in the study - please complete EXIT form)				Yes 	No 
Study Phase	geko™ Device Fitted		Lot Number	Expiry Date	
Phase 1		geko™ T3			
Phase 2		geko™ X-T3			

CASE REPORT FORM	FOLLOW-UP 1 (DAY 1)			DATE (DD/MM/YYYY)	/	/
STUDY SITE: THE ROYAL STOKE UNIVERSITY HOSPITAL	PRINCIPAL INVESTIGATOR: [name]					

SITE NUMBER

0	2	5
---	---	---

 PATIENT NUMBER

0		
---	--	--

 PATIENT INITIALS

--	--

How easy was it to apply the geko™ device to the patients leg?

Very Easy 	Easy 	Difficult 	Very Difficult 	Impossible 
---------------------------------------	----------------------------------	---------------------------------------	--	--

If there were any difficulties, please provide a comment below:

Once applied, how comfortable for the patient was the geko™ device?

Very Comfortable 	Comfortable 	Uncomfortable 	Very Uncomfortable 	Extremely Uncomfortable 
--	---	---	--	---

If any discomfort has been indicated, please provide a comment below:

Which setting was the geko™ device set to?

1 	2 	3 	4 	5 	6 	7 	8 	9 	10 	11 

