-------------------------------	-------------------------------	-------------------------------	-------------------------------	-------------------------------	-------------------------------	-------------------------------	-------------------------------	-------------------------------	--------------------------------	--------------------------------

Has the patient experienced any Adverse Events since signing the Informed Consent?

Yes No

If yes, please comment below:

CRF completed by:

Print Name: _____ Signature: _____ Date: ____/____/_____

To be completed by Principal Investigator:

I am confident that the information supplied in this case record form is complete and accurate data.

Signature: _____ Date: ____/____/_____

Final Follow-up Day 10

CASE REPORT FORM	FINAL FOLLOW-UP 10 (DAY 10)			DATE (DD/MM/YYYY)	_____/_____/_____					
STUDY SITE: PRINCIPAL INVESTIGATOR:	THE ROYAL STOKE UNIVERSITY HOSPITAL [name]									
SITE NUMBER	0	2	5	PATIENT NUMBER	0			PATIENT INITIALS		

How many hours did the patient wear the geko™ device for?					_____ hours
How well did the geko™ device stick to the patient's leg?					
Very Well Remained attached 	Well Detached in small area 	Poorly Detached over large area 	Very Poorly Detached completely 	Not at all Would not stick at all 	

If any level of detachment has been indicated, please provide a comment below:

Did the patient need any additional fixation to keep the geko™ device in position?				
None 	Micropore Tape 	Adhesive Accessory 	OnPulse™ Knee Strap 	

If removed was the geko™ device easily re-applied?				
Yes 	No 	N/A 		

If no, please comment below:

Overall, how comfortable was the geko™ device for the patient to wear?				
Very Comfortable 	Comfortable 	Uncomfortable 	Very Uncomfortable 	Extremely Uncomfortable 

If any discomfort has been indicated, please provide a comment below:

Did the patient sleep with the device on?	Yes 	No 
---	------------------------------	-----------------------------

Any other comments – please add below

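### Day 10 has no adverse-event question in section 4.3, on the Day 10 form or on the Exit form, although Table 1 schedules AE assessment for Days 1-10

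*Combined protocol and SAP*

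**What the plan says.** **Schedule.** Table 1 has a row "Assess for AEs", marked at baseline and under a single follow-up column that covers Days 1-10. Section 7.4 also includes AE assessment among the items gathered "for a maximum of 10 days or until the patient is able to mobilize independently".

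**Visit lists.** Sections 4.1 (Day 0) and 4.2 (Days 1-9) each end with an AE item. Section 4.3 (Day 10) begins "At the final follow-up, the following information will be collected" and names hours of wear, adhesion, extra fixation, re-application, comfort, sleep and mobility. It then closes the patient's participation and points to Table 1 for the complete schedule.

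**Forms.** In Appendix 3 the Baseline and Days 1-9 forms ask "Has the patient experienced any Adverse Events since signing the Informed Consent". The Day 10 form has no such question. Its last item is "Any other comments – please add below", after which staff go to the Exit form, which takes dates, the last assessment done and a reason for leaving. Section 10.0 states: "All CRFs for the study, can be found in Appendix 3 of this protocol".

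**Use of the data.** Sections 2.1.2 and 8.4.2 make the secondary endpoint the incidence of AEs, serious AEs, treatment-related AEs and device-related AEs, summarised descriptively.

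**The concern.** The schedule and the working instructions disagree about the last visit. Staff who follow section 4.3 and the supplied forms will not ask a completing patient about AEs on Day 10. No later contact could make good the omission.

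What is at stake is completeness of the secondary endpoint. Lower skin irritation is part of the reason for developing the new hydrogel (section 1.3), and skin inflammation or irritation is the side effect named in the instructions for use (Appendix 4). A reaction that first shows while the last device is on, or when it comes off, is an event this endpoint should count.

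**Working it through.** **Step 1: text and forms side by side.**

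| Visit | Visit list | Form | Table 1 |
|---|---|---|---|
| Day 0 | AE item (4.1) | AE question | marked |
| Days 1-9 | AE item (4.2) | AE question | marked |
| Day 10 | none (4.3) | none | marked (merged Days 1-10 column) |
| Exit | no list | none | no column |

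Day 10 is the only scheduled visit without the item. The likely cause is visible in the layout. Section 4.2 has a look-back list followed by a list for the newly fitted device, and the AE item closes the second list. Section 4.3 keeps the look-back list and drops the second, which is sensible for fitting items because no device is fitted on Day 10. The AE item went with them. The forms show the same cut.

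**Step 2: count the intervals.** A device is fitted on Day d and reviewed on Day d+1, for d = 0 to 9. That gives 10 wear intervals for a patient who reaches Day 10. AE questions are asked on Days 0 to 9, so the last one comes at the end of interval 9 (Day 8 to Day 9).

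- Intervals with an AE question at or after their end: 9 of 10.
- Intervals without one: 10 − 9 = 1 of 10 (Day 9 to Day 10).
- With an AE question on the Day 10 form: 10 of 10.

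The question runs from consent onwards, so an event missed on one day can still be picked up on a later day up to Day 9. Only events that first appear after the Day 9 question are exposed.

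**Step 3: scale to a cohort.** With k completers, k of 10k completer intervals are affected. The plan does not say how many patients will reach Day 10. If all 20 in a cohort did (an assumption), it would be 20 of 200, or 40 of 400 over both cohorts. Fewer completers means fewer affected intervals.

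**Step 4: early exits.** On the Days 1-9 form the mobility item carries the instruction "If YES is selected patient CANNOT continue in the study - please complete EXIT form". The AE question comes later on that form, after the lot details and three items on a newly fitted device, the last being "Which setting was the geko™ device set to". Nothing tells staff to skip the AE question, and nothing tells them to answer it before turning to the Exit form. The last interval of such a patient is exposed only if staff stop at the instruction.

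**Step 5: events lost.** This would need an AE rate per interval and a capture rate for the indirect routes. The documents give neither.

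**The case against.** **Table 1 is coarse.** Its follow-up column also marks device fitting, ease of fitting and device setting, none of which occurs on Day 10, and its baseline column marks hours of wear and sleep, which section 4.1 does not collect. The mark is thus imperfect evidence of a deliberate Day 10 requirement. This stands as a caution. But AE assessment, unlike fitting, does not depend on a new device, and the last device is worn up to Day 10. If Table 1 does govern, because section 4.3 refers to it, Day 10 assessment is already required and the form fails to support it.

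**Section 7.4 is weak support.** Ten days can be read as Days 0-9, and its list also contains fitting items. Accepted; the point does not depend on it.

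**Other routes exist.** The Day 10 form asks about overall comfort and requests a comment on any discomfort, which bears directly on skin irritation. There is also the general comments box, the 24-hour report of device-related events (section 9.1), and form review against the medical record (sections 11.2 and 13.1). A reader might infer that a late event goes wholly unprompted; the documents do not support that. What is missing is an AE-specific question. The routes are indirect, and the 24-hour report does not cover unrelated, non-serious events, which the endpoint counts.

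**The appendix may be incomplete.** It is headed as sample forms, and section 11.4 wants deviations documented in the forms although no field for them is shown. Section 10.0 nevertheless says the full set is there, and section 4.3 has the same omission.

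**Early walkers.** A reader might infer that they leave without being asked. That is not established: their form contains the question, has no skip instruction, and is signed by the investigator as complete.

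**Conclusion.** The inconsistency is real and of minor priority. For a Day 10 completer, 1 of 10 wear intervals has no AE-specific question after it, and AE incidence may be slightly under-counted as a result. The count assumes daily refitting on Days 0-9 and use of the forms as printed.

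Two stronger readings should be resisted. The first is a figure for events lost. Any such figure would rest on an assumed event rate; a calculation that counts only each patient's first AE would not be an upper bound either, because serious, treatment-related and device-related events are counted separately and may follow an earlier unrelated one. The second is bias towards one device. Both cohorts use the same forms, so the gap by itself lowers the count in both and favours neither.

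The priority is minor because the study's objective is adhesion, the AE summary is descriptive, the patients are inpatients reviewed daily, and the indirect routes will catch some events.

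**What to change.** 1. Add an AE assessment bullet to the section 4.3 list.
2. Put the existing question, "Has the patient experienced any Adverse Events since signing the Informed Consent", on the Day 10 form.
3. As a low-cost safeguard for early exits, add a line to the mobility item on the Days 1-9 form saying that the AE question is answered before the Exit form is completed.

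This raises AE-prompted intervals for a completer from 9 of 10 to 10 of 10. It adds no visit and no analysis, and leaves the sample size unchanged. The cost is a small amendment to the protocol and forms, which may need ethics approval before use (sections 11.3 and 12.1), and a reported AE count that may be slightly higher in both cohorts.
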